The purpose of the Protocol Amendment 3 is to improve participant adherence to the vaccination schedule by increasing time interval between Visit 1 (first study vaccination) and Visit 5 (third study vaccination) that will allow participants to complete HPV vaccination series during the study period. Additionally, for the analysis of anti-HPV neutralizing antibody titers at Month 2, we increased the number of participants from 160 up to 384 to collect additional immunogenicity data after the first study vaccine administration. This change applies to samples already collected and no additional Month 2 blood samples will be collected from participants. Furthermore, a change has been made in the statistical section to obtain group data (i.e., HPV9High, HPVMed and HPVLow study groups) instead of pooled data on correlation between anti-HPV IgG antibody concentration and anti-HPV neutralizing antibody titers.

Added text is **bold italic** and deleted text is strikethrough.

Section and Name	Description of Change	Brief Rationale
1.1 Synopsis,3.0 Objectives and endpoints,	Edited text in footnote #3: Anti-HPV neutralizing antibody titers at Month 2 will be performed in a subset of 160 384 participants (at least 40 96 participants in each group)	Increase the pool of immunogenicity data after the first vaccine administration
1.3 Schedule of Activities	Table 2 Intervals Between Study Visits Allowed Interval Range Visit 1 → Visit 5 180166-194 days	Improve participants' adherence to the vaccination schedule and ensure completion of a full HPV vaccination series
4.1 Overall Design,	Edited text:	Increase immunogenicity data after

Section and Name	Description of Change	Brief Rationale
Appendix 3	Pseudovirion-based neutralization assay (PBNA) at () Month 2 will be performed in a subset of 160 384 participants (at least 40 96 participants in each group)	the first vaccine administration
9.4.2.2.1 Within Groups Assessment	Edited text: Pearson coefficient of correlation between anti-HPV IgG antibody concentration and anti-HPV neutralizing antibody titers with associated P-value will be calculated for eachpooled investigational adjuvanted vaccines group and Gardasil 9 group for each antigen for timepoint and overall.	To obtain group data instead of pooled data on correlation between anti-HPV IgG antibody concentration and anti-HPV neutralizing antibody titers

1. PROTOCOL SUMMARY

1.1. Synopsis

Protocol Title: A Phase 1/2 randomized, observer-blinded, multi-country study to evaluate safety and immunogenicity of investigational adjuvanted human papillomavirus vaccine in females (16 to 26 years of age)

Protocol Number: 213749 (HPV9-AS04-001)

Protocol Amendment Number: 3

Product: investigational adjuvanted human papillomavirus vaccine

Short Title: A study on the immune response and safety of a human papillomavirus vaccine when given to healthy women 16 to 26 years of age.

Rationale: GlaxoSmithKline Biologicals SA (GSK) is developing an investigational adjuvanted human papillomavirus (HPV) vaccine to protect against HPV types 6, 11, 16, 18, 31, 33, 45, 52, and 58. This study will evaluate the reactogenicity, safety, and immunogenicity of 3 formulations of GSK's investigational adjuvanted HPV vaccine versus *Gardasil 9*, administered intramuscularly (IM) according to a 0, 2, 6 month vaccination schedule in females 16-26 years of age.

Primary and Secondary Objectives and Endpoints

Objectives	Endpoints
formulations	after the third dose (Month 7).
Secon	ndary
To evaluate the safety and reactogenicity of GSK's investigational adjuvanted HPV vaccine formulations	 Solicited events Percentage of participants reporting each solicited administration site event within 7 days (Day 1 – Day 7) after each vaccine dose. Percentage of participants reporting each solicited
	systemic event within 7 days (Day 1 – Day 7) after each vaccine dose.
	Unsolicited AEs
	Percentage of participants reporting unsolicited symptoms within 28 days (Day 1 – Day 28) after each vaccine dose
	Potential immune-mediated disease (pIMDs)
	Percentage of participants reporting pIMDs from first vaccination up to study end.
	Pregnancy outcomes
	The percentage of participants who experienced pregnancy and their outcomes from Day 1 of pregnancy up to study end.
To evaluate the immune response for all HPV vaccine types for all vaccines	Anti-HPV IgG antibody concentration at Day 1, Month 2, Month 3, Month 6, Month 7 and Month 12.
	Anti-HPV IgG antibody seroconversion ¹ rate at Month 2, Month 3, Month 6, Month 7 and Month 12.
	• Anti-HPV neutralizing antibody titers at Day 1, Month 3 and Month 7 ² in all participants, Month 2 ³ in a subset of participants.
	• Anti-HPV neutralizing antibody seroconversion ¹ rate at Month 3 and Month 7 ² .
	Correlation between anti-HPV IgG antibody concentration and anti-HPV neutralizing antibody titers at Day 1, Month 2, Month 3 and Month 7.

¹ Seroconversion is defined as the appearance of antibodies (i.e., concentrations/titer greater than or equal to the cut-off value) in the serum of participants seronegative before vaccination.

Note: Tertiary objectives and endpoints are available in the main text of this protocol.

Overall Design: This will be a phase 1/2 randomized, observer-blind, multi-country study with 4 groups of females 16-26 years of age at the time of vaccine administration. Participants will be

² At least 150 participants in each group. In case of any delay, analysis may be performed for as many participants as possible with data available at the time of the analysis. Analysis for remaining participants will be performed at the time of the next analysis.

³ 384 participants (at least 96 participants in each group)

randomized in a 1:1:1:1 ratio to receive a series of 3 investigational adjuvanted intervention doses (3 different potencies [a high, medium, low potency]) or a series of the *Gardasil 9* vaccine. The investigational adjuvanted intervention or *Gardasil 9* vaccine will be administered intramuscularly (IM) at Day 1 (Month 0), Month 2, and Month 6. Blood sampling will be performed on Day 1, Month 2, Month 3, Month 6, Month 7, and Month 12 to assess for immunological response. In Germany, only adult participants between and including 18 years to 26 years of age are to be included in this clinical study.

This study is organized in to 2 steps. Forty-eight participants (12 per group) of the study Step 1 (sentinel participants) will receive the initial assigned dose prior to participants in Step 2 of the study, and sentinel participants will have an additional blood sampling visit at Day 7 to assess for biochemical and hematological parameters. The internal Safety Review Committee (iSRC) will review the accumulated safety data up to 7 days post-dose 1 for the sentinel participants* to determine whether any of the pre-defined holding rules have been met. If no safety concerns were observed and no holding rules were met, the sentinel participants will continue with study visits and dosing as scheduled and the Step 2 participants will be initiated. Vaccination of Step 2 participants with a second dose will not be initiated before all Step 1 participants have received their second vaccination dose.

*In case not all 48 of the Step 1 participants are enrolled and vaccinated with a first dose of study vaccine by 30 September 2022, the iSRC will review the accumulated safety data up to 7 days post-dose 1 of all participants available by that date. If no safety signal is identified, these participants will be vaccinated with a second dose. To avoid any additional participants running out of the allowed interval range for their second vaccine dose, additional iSRC review(s) may need to be planned to review the safety data up to 7 days post-dose 1 of these participants, but only when all 48 Step 1 participants have been enrolled and their data have been reviewed by the iSRC, the iSRC will decide on the initiation of the vaccination of Step 2 participants.

Number of Participants: Approximately 1080 participants will be randomly assigned to the 4 study groups to provide approximately 270 participants per study group.

Intervention Groups:

Study groups	Study Interventions	Number of Participants
HPV9High	HPV9-High	270
HPV9Med	HPV9-Medium	270
HPV9Low	HPV9-Low	270
Gar9	Gardasil 9	270

Duration: The duration of the intervention will be approximately 6 months. Participants will be monitored until Month 12. Monitoring of pregnancies (if any) can be beyond 12 months.

Statistical Methods: Three analyses sets will be used in this study, the Enrolled Set, the Exposed Set, and the Per Protocol Set. The primary objective and all immunogenicity objectives will be evaluated descriptively. Exploratory immunologic non-inferiority analyses will be performed, to help in decision making of the formulation selection for the further phase 3 clinical studies.

Internal Safety Review Committee: An iSRC will be reviewing the accumulated safety data up to 7 days post-dose 1 for the sentinel participants to determine whether any of the pre-defined holding rules have been met in order to proceed with study schedule of activities. The iSRC will review the safety data on a monthly basis until safety data from 1-month post-dose 2 for all participants and data from 1-month post-dose 3 for Step 1 participants are reviewed.

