9.4.2.2.1. Within Groups Assessment

For each group at each time point for which a blood sample result is available, the following analyses will be conducted:

- Seroconversion and seropositivity rates for each antigen (with exact 95% CI) will be calculated.
 - Seroconversion is defined as the appearance of antibodies (i.e., concentrations/titer greater than or equal to the cut-off value) in the serum of participants seronegative before vaccination.
- Antibody GMCs/GMTs with 95% CI and range of antibody concentrations/titers will be tabulated for each antigen.

- The antibody GMCs will be derived considering log-transformed concentrations are normally distributed with unknown variance. Concentration below the assay cut-off will be assigned half the cut-off for the purpose of antibody GMC computation.
- The distribution of antibody concentrations/titers for each antigen will be displayed using reverse cumulative curves for the sub-cohort of initially seronegative participants.
- Pearson coefficient of correlation between anti-HPV IgG antibody concentration and anti-HPV neutralizing antibody titers with associated P-value will be calculated for each investigational adjuvanted vaccines group and *Gardasil 9* group for each antigen for timepoint and overall. The Pearson correlation coefficient is computed by log₁₀ transformation of specific antibody concentrations. Scatter plots will be generated.
- For each HPV type, the functional relationship between the pair of assay methods (pseudovirion-based neutralization assay [PBNA] versus ECL) will be estimated by timepoint using the Deming's regression model (Brown et al, 2014).

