7.6. Common Calculations

Geometric Mean Concentration/Titer (GMC/GMT):

Distributions of antibodies are generally skewed to the right (Nauta, 2010). Therefore, prior to any statistical analysis that assumes normally distributed observations, antibody concentrations or titers will be log10-transformed. GMC/GMTs and their 95% CI are computed by exponentiating (base 10) the least squares mean and 95% CI of the log10 titers.

Document: \\quintiles.net\Enterprise\Apps\sasdata\SASb\SAS\GlaxoSmithKline\HPV\213749

(HPV9)\Biostatistics\Documentation\SAP\GSK 213749(HPV9-AS04-

001)_WZA97329_SAP_Final_v3.0_02FEB2024.docx

Author: PPD Version Number: 3.0

Version Date: 02FEB2024

Template No.: CS_TP_BS016 Revision 7 Reference: CS_WI_BS005

Page 29 of 48

The GMC/GMT will be calculated using the following formula:

$$10^{\left(\frac{\sum_{i=1}^{n}\log 10(t_i)}{n}\right)}$$

Where $t_1, t_2, ..., t_n$ are n observed immunogenicity concentrations/titer.

Concentration below assay cut-off (i.e., <lower limit of quantification or < LLOQ) will be replaced by half the assay cut-off (LLOQ/2) for the purpose of GMC computation. Any concentrations above the upper limit of quantification (or ULOQ) will be set to the ULOQ value. No imputation for ULOQ will be performed for the sensitivity analysis of GMC/GMT and for the correlations and Deming's regression.

Seroconversion:

Defined as the appearance of antibodies (i.e., concentrations/titers greater than or equal to the cut-off value) in the serum of participants seronegative before vaccination.

For quantitative measurements, change from baseline will be calculated as:

• Test Value at Visit X – Baseline Value

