Seroconversion is defined as the appearance of antibodies (i.e, titers greater than or equal to the LLOQ) in the serum of participants seronegative before vaccination

Table 14.2.2.5

Differences of anti-HPV Neutralizing Antibody Seroconversion Rate for each antigen at Month 3 and Month 7 between Groups (HPV group [different potencies - Low, Med, High] and Gardasil9 group)

Per Protocol Set

Antigen: xxx (LLOQ = xx; ULOQ = xx; Unit = xx)

-			First	Study Group	Second	d Study Group	Dif	ference
			N	n (%)	N	n (%)	%	95% CI

95% CI = 95% CI computed based on Miettinen and Nurminen method.

The titer below the LLOQ will be replaced by half the LLOQ (LLOQ/2). Titer above the ULOQ will be replaced by the ULOQ.

Programming Notes

Document: \\quintiles.net\Enterprise\Apps\sasdata\SASb\SAS\GlaxoSmithKline\HPV\213749 (HPV9)\Biostatistics\Documentation\SAP\Shells\\GSK 213749(HPV9-AS04-001) WZA97329_TFL Shells_V3.0_05FEB2024.docx

Author: Version Number: 3.0

Table 14.2.2.6: Correlation between anti-HPV Immunoglobulin Antibody Concentration and anti-HPV Neutralizing Antibody Titers for each antigen at Day 1, Month 2, Month 3 and Month 7 (Per Protocol Set)

GSK Vaccines Page X of Y

Study 213749 - DELIVERY DESIGNATION

Table 14.2.2.6

Correlation between anti-HPV Immunoglobulin Antibody Concentration and anti-HPV Neutralizing Antibody Titers for each antigen at Day 1, Month 2, Month 3 and Month 7

Per Protocol Set

Antigen: xxx

			Pearson coefficie	ent of
Study Dose	Visit	n	correlation	p-value
HPV9 High	Day 1	xx		0.xxx
IIE V 9 III GII	Month 2	XX	x.xxx	0.xxx 0.xxx
	Month 3	XX	X.XXX	
			X.XXX	0.xxx
	Month 7	XX	X.XXX	0.xxx
	Overall	xx	x.xx	0.xxx
HPV9 Medium	Day 1	xx	x.xxx	0.xxx
	Month 2	XX	x.xxx	0.xxx
	Month 3	XX	x.xxx	0.xxx
	Month 7	XX	x.xxx	0.xxx
	Overall	XX	X.XXX	0.xxx
•••				

Source: Listing xx.x.x.x

Abbreviations: HPV = Human Papillomavirus.

n is the number of samples with both concentration and titer values.

Pearson correlation will be computed by the log10-transformation of the antibody concentration. Samples testing below the LLOQ or above the ULOQ in either assay were excluded from the analysis.

Programming Notes

Document: \\quintiles.net\Enterprise\Apps\sasdata\SASb\SAS\GlaxoSmithKline\HPV\213749 (HPV9)\Biostatistics\Documentation\SAP\Shells\

GSK 213749(HPV9-AS04-001)_WZA97329_TFL Shells_V3.0_05FEB2024.docx

Author: Version Number: 3.0

GlaxoSmithKline Biologicals SA PROTOCOL 213749 (HPV9)

Output ID: IM0007

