[Source: \\quintiles.net\Enterprise\Apps\sasdata\SASb\SAS\GlaxoSmithKline\HPV\213749

(HPV9) \Biostatistics\Filename.sas] IQVIA DDMMMYYYY HH:MM

\\quintiles.net\Enterprise\Apps\sasdata\SASb\SAS\GlaxoSmithKline\HPV\213749 (HPV9)\Biostatistics\Documentation\SAP\Shells\ Document: GSK 213749(HPV9-AS04-001)_WZA97329_TFL Shells_V3.0_05FEB2024.docx

Version Number: 3.0 Author:

Table 14.2.2.7: Functional Relationship between the Assay Methods for each antigen (Per Protocol Set)

GSK Vaccines Page X of Y

Study 213749 - DELIVERY DESIGNATION

Table 14.2.2.7
Functional Relationship between the Assay Methods for each antigen
Per Protocol Set

Antigen: xxx					
Study Dose	Visit	n	Intercept (95% CI for		
			Intercept)	Slope (95% CI for slope)	
IPV9-High	Day 1	xxx	xx.xx (xx.xx, xx.xx)	xx.xx (xx.xx, xx.xx)	
ii və iiigii	Month 2		xx.xx (xx.xx, xx.xx)	xx.xx (xx.xx, xx.xx)	
	Month 3	XXX			
		XXX	xx.xx (xx.xx, xx.xx)	xx.xx (xx.xx, xx.xx)	
	Month 7	XXX	xx.xx (xx.xx, xx.xx)	xx.xx (xx.xx, xx.xx)	
	Overall	xxx	xx.xx (xx.xx, xx.xx)	xx.xx (xx.xx, xx.xx)	
IPV9-Medium	Day 1	xxx	xx.xx (xx.xx, xx.xx)	xx.xx (xx.xx, xx.xx)	
	Month 2	xxx	xx.xx (xx.xx, xx.xx)	xx.xx (xx.xx, xx.xx)	
	Month 3	xxx	xx.xx (xx.xx, xx.xx)	xx.xx (xx.xx, xx.xx)	
	Month 7	xxx	xx.xx (xx.xx, xx.xx)	xx.xx (xx.xx, xx.xx)	
	Overall	xxx	xx.xx (xx.xx, xx.xx)	xx.xx (xx.xx, xx.xx)	
HPV9-Low		xxx	xx.xx (xx.xx, xx.xx)	xx.xx (xx.xx, xx.xx)	

Source: Listing xx.x.x.x

Abbreviations: HPV = Human Papillomavirus. ECL = Electrochemiluminescence assay. PBNA = Pseudovirion-Based Neutralization Assay

n is the number of samples with both concentration and titer values.

Deming's regression model is fitted to the Anti-HPV IgG antibody concentration (ECL) with Anti-HPV Neutralizing titers (PBNA) as a covariate.

Deming's regression will be computed by the log10-transformation of the antibody concentration and neutralizing titer. Samples testing below the LLOQ or above the ULOQ in either assay were excluded from the assay.

Document: \\quintiles.net\Enterprise\Apps\sasdata\SASb\SAS\GlaxoSmithKline\HPV\213749 (HPV9)\Biostatistics\Documentation\SAP\Shells\

GSK 213749(HPV9-AS04-001) WZA97329 TFL Shells V3.0 05FEB2024.docx

Author: Version Number: 3.0

Antigen: xxx

Study Dose	Visit	n	Intercept (95% CI for	
			Intercept)	Slope (95% CI for slope)

Programming Notes

Output ID: IM0008

[Source: \\quintiles.net\Enterprise\Apps\sasdata\SASb\SAS\GlaxoSmithKline\HPV\213749

(HPV9)\Biostatistics\Filename.sas] IQVIA DDMMMYYYY HH:MM

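### The correlation and Deming shells drop every sample outside either assay's range, a rule the SAP text does not state; it lowers r after vaccination and can move the slope either way.

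*Protocol*

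**What the plan says.** Protocol 1.1 and Table 4 list as a secondary endpoint the "Correlation between anti-HPV IgG antibody concentration and anti-HPV neutralizing antibody titers at Day 1, Month 2, Month 3 and Month 7". Protocol 9.4.2.2.1 introduces the within-group analyses with "For each group at each time point for which a blood sample result is available, the following analyses will be conducted". It plans a Pearson coefficient on log10 values for each group and a Deming regression by time point. Its only rule for values outside the assay range is for another quantity: "Concentration below the assay cut-off will be assigned half the cut-off for the purpose of antibody GMC computation".

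SAP 16.2.3.5 repeats the plan, fits the Deming model separately by antigen and study group with an error ratio of 1, and reads a slope close to 1 as agreement between the assays. It names no exclusion. SAP 7.6 adds: "No imputation for ULOQ will be performed for the sensitivity analysis of GMC/GMT and for the correlations and Deming's regression". SAP 16.4 runs the correlation again as a sensitivity analysis, with values above ULOQ left unimputed.

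The shells go further. The footnote of Table 14.2.2.6 (Pearson) reads "Samples testing below the LLOQ or above the ULOQ in either assay were excluded from the analysis"; that of Table 14.2.2.7 (Deming) reads "Samples testing below the LLOQ or above the ULOQ in either assay were excluded from the assay". Figure 16.1.2.3 carries the same rule. Both tables also define n as the number of samples that have a concentration and a titer.

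**The concern.** Three things do not fit together. The rule that decides which samples enter a secondary endpoint appears only in output footnotes. The n to be printed is by its definition larger than the number analysed whenever a sample is excluded. And the sensitivity analysis cannot differ from the main one: SAP 7.6 already leaves values above ULOQ unimputed in the main correlation, and under the shells those samples are gone.

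The rule also has a statistical effect. Choosing samples by the values of the two variables being correlated is truncation, which reduces r when the data are roughly bivariate normal on the log scale. If the two assays are cut unequally, or their SDs differ, it also changes the Deming slope. Results are reported by formulation and visit, so groups with different shares out of range can show different r and slope although the assays relate in the same way in each.

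**Working it through.** The documents state no expected correlation, slope or out-of-range share, so there is no planned figure to reproduce.

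**Inputs.** SD of log10 IgG 0.7 and of log10 neutralizing titer 0.6 (Protocol 9.2.2.1, planning values for power). Error ratio 1 (SAP 16.2.3.5). Assumed: true r = 0.80, bivariate normal logs, share q above ULOQ. LLOQ and ULOQ are placeholders in the shells.

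**Step 1: effect on r, one assay cut.** Let z be the normal quantile at 1 − q and λ = φ(z)/(1 − q). The cut assay keeps a fraction k = 1 − zλ − λ² of its variance. The covariance is also multiplied by k, and the other assay's variance by g = 1 − r²(1 − k). Hence r after exclusion = r·√(k/g).

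For q = 20%: z = 0.8416, λ = 0.3500, k = 0.583, g = 1 − 0.64 × 0.417 = 0.733, so r = 0.80 × √(0.583/0.733) = 0.71.

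| Share above one ULOQ | k | g | r |
|---|---|---|---|
| 5% | 0.810 | 0.878 | 0.77 |
| 10% | 0.712 | 0.816 | 0.75 |
| 20% | 0.583 | 0.733 | 0.71 |
| 30% | 0.493 | 0.675 | 0.68 |

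With 20% above ULOQ in both assays, simulation gives r = 0.69.

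**Step 2: effect on the Deming slope.** With x = log PBNA and y = log ECL, slope = [Syy − Sxx + √((Syy − Sxx)² + 4Sxy²)] / (2Sxy).

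- No exclusion: Sxx = 0.36, Syy = 0.49, Sxy = 0.8 × 0.42 = 0.336; slope = (0.13 + 0.6845)/0.672 = 1.21.
- 20% cut, ECL only: Sxx = 0.36 × 0.733 = 0.264, Syy = 0.49 × 0.583 = 0.286, Sxy = 0.336 × 0.583 = 0.196; slope = (0.022 + 0.392)/0.392 = 1.06.
- 20% cut, PBNA only: Sxx = 0.210, Syy = 0.359, Sxy = 0.196; slope = (0.149 + 0.419)/0.392 = 1.45.
- 20% cut in both (simulation): 1.25.

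With equal SDs the slope is 0.85 (ECL only), 1.17 (PBNA only) and 1.00 when both assays are cut at the same quantile.

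**Step 3: two groups with the same assay relationship.** If 5% of one group and 20% of another exceed the ECL ULOQ, r is 0.77 against 0.71, and the same slope formula with the planning SDs gives 1.16 against 1.06.

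**Step 4: which groups are affected.** In simulation with the planning SDs and both limits fixed, a mean shift of +0.7 log10 takes r from 0.76 to 0.66 under a ULOQ cut, but from 0.66 to 0.75 under an LLOQ cut.

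**Step 5: Day 1.** If 10–30% of participants are truly seropositive (assumption), exclusion keeps about 8–25% of samples. With 10% seropositive, r after exclusion is 0.73 against 0.94 with negatives kept at LLOQ/2 when no pair is discordant, but 0.72 against 0.50 when 30% of the negatives are discordant.

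**Step 6: an all-pairs alternative.** With 20% above ULOQ and out-of-range values tied at the limit, Spearman is 0.78, against 0.79 on complete data.

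**The case against.** The strongest defence is that the rule is pre-specified and sensible. SAP 9 makes the templates part of the plan, all three outputs state the same exclusion, and not imputing is compatible with excluding. Seronegative and discordant samples are not lost: SAP 16.2.4.5 and Table 14.2.2.8 analyse every pair by agreement rate, kappa and McNemar, including at Day 1. Tables 14.2.1.1 and 14.2.2.3 print counts at or above LLOQ and above ULOQ for each assay. The immunogenicity objectives are descriptive, and no test compares r or slope between groups.

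Much of this stands and limits the point. But the agreement analysis uses serostatus only, so it cannot show how far r or slope was changed, and counts for each assay do not give the number of pairs excluded. Pre-specifying a rule does not remove its bias.

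Several stronger readings are tempting and not supported:

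- That the protocol requires every result to enter the correlation. The clause on available results in 9.4.2.2.1 qualifies time points; the protocol is silent on range, so the shells do not contradict it and their absence from SAP 4.3 is not a breach.
- That the highest-titer groups always lose most. This holds for the ULOQ cut and reverses for the LLOQ cut.
- That the slope falls, or that the rule works against a favorable reading. It can rise, fall or stay put; a 20% ECL-only cut brings 1.21 closer to 1.
- That r is always lowered. At Day 1 the direction is not fixed.

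**Conclusion.** The point holds as an inconsistency between SAP text and shells with a real bias behind it. After vaccination, the exclusion lowers r from an assumed 0.80 to about 0.75, 0.71 or 0.68 for 10, 20 or 30% above one assay's ULOQ. It moves the slope in a direction that depends on which assay is cut and on the SDs. Differences in r or slope between groups or visits can therefore reflect the share of samples out of range.

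These sizes rest on the assumed true r, bivariate normal logs and assumed out-of-range shares; if few samples fall outside the limits, the effect is small. The planned formulation comparison, non-inferiority on GMC ratios, is not touched. The matter deserves correction before the correlation results are interpreted, but it does not threaten the trial's main conclusions.

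**What to change.** 1. State one rule for out-of-range values in the correlation and Deming regression, worded the same in SAP 7.6, SAP 16.2.3.5 and the three shells.
2. Define n as the samples analysed. Print the number of pairs excluded by group, visit and reason (below LLOQ or above ULOQ, by assay).
3. Keep the in-range Pearson and Deming results, and replace the redundant correlation run in SAP 16.4 with an all-pairs analysis. Spearman with out-of-range values tied at the limits is the simplest. A censored-likelihood fit is an option for post-vaccination visits only: Day 1 is a mixture of serostatus, and a bivariate log-normal fit to 270 simulated women, 10% of them positive with a true r of 0.70 among the positives, gave about 0.98.
4. Do not interpret between-group differences in r, or a slope near 1, without that analysis.

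The cost is wording, extra count rows and one more coefficient per antigen, group and visit, with no new data. The censored fit, if chosen, adds a distributional assumption. Spearman answers for r only, so without the censored fit the slope is read from the in-range data with the exclusion counts beside it.
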